16.1.3. Relationship to Study Medication

Relationship, as indicated by the Investigator, is classed as “not related”, “possible”, “probable” (increasing severity of relationship) or “definite”.

For summaries by relationship to the study medication, AEs will be grouped as “related” or “not related.”

- AE Related: AEs with relationship to study medication assessed as “possible,” “probable,” or “definite”
- AE not Related: AEs with relationship to study medication assessed as “not related”
- AEs with a missing relationship to study medication will be regarded as related

If a subject report the same AE more than once within that SOC/ PT, the AE with the worst-case relationship to study medication will be used in the corresponding relationship summaries.

16.1.4. AEs Leading to Discontinuation of Study Medication

For AEs leading to discontinuation of study medication, summaries of incidence (numbers and percentages) by SOC and PT will be provided.

Listing of AEs leading to discontinuation will be provided.

16.1.5. Serious Adverse Events

Serious adverse events (SAEs) are those events recorded as “Serious” on the Adverse Events source.

Incidence of SAEs and number of events will be presented by arm, SOC and PT.

All SAEs will be summarized overall and by age group, race group, gender, baseline AEDs and number of baseline AEDs.

Additionally, listing of SAEs will be provided.

16.1.6. Non-Serious Adverse Events

Incidence of non-SAEs and number of events will be presented by arm, System Organ Class (SOC) and Preferred Term (PT).

16.1.7. Adverse Events Leading to Death

AEs leading to Death are those events which are recorded with outcome of "Fatal" on the Adverse Events source. A summary of AEs leading to death by SOC and PT will be prepared.

Listing of deaths will be provided.

16.2. Laboratory Evaluations

Results from the central laboratory will be included in the reporting of this study for Hematology, Blood Chemistry, Urinalysis, Thyroid Panel, Renal Functioning, Urine Drug Screening, Serum Pregnancy and Urine Pregnancy Test. A list of laboratory assessments to be included in the outputs is included in Appendix 1 of the protocol, Section 20.

All laboratory summaries will be used on the safety population and presentations will use SI Units.

Quantitative laboratory measurements reported as "< X", will be converted to X for the purpose of quantitative summaries, but will be presented as recorded, i.e. as "< X" or "> X" in the listings. The following summaries and listings will be provided for laboratory data:

- For laboratory parameters with continuous outcomes (e.g. blood chemistry, hematology, urinalysis data, thyroid panel), descriptive statistics for the actual values and for changes from baseline will be presented by arm for each evaluation time point.
- For laboratory parameters with categorical outcomes (e.g. urinalysis data), the number and percentage of subjects with each outcome will be presented by arm at each evaluation time point.
- Overall summary of the post-baseline PCS will be presented. The number and percentage of subjects with PCS criteria will be summarized by arm . This summary will be also

presented by age group, race group, gender, baseline AEDs and number of baseline AEDs.

- Shifts from baseline by arm for each evaluation time point will be produced to show the percentage of subjects with laboratory test values below, within, and above the normal range.
- Data listing of all clinical laboratory measurements (hematology, blood chemistry, urinalysis, thyroid, and renal function) will be provided. Results outside of the reference range will be flagged.
- Listing of clinically significant out of range laboratory measurements, urine drug screen and serum pregnancy test results will be provided.
- A listing of PCS laboratory findings (e.g. blood chemistry, hematology, urinalysis data, and thyroid function) will be presented for all laboratory parameters with PCS criteria defined in Appendix 3.

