6.4. Retests, Unscheduled Visits and Early Discontinuation Visit (EDV)

In general, for by-visit summaries, data recorded at the nominal visit will be presented including visit 9 (EOS) and EDV. Unscheduled measurements collected prior to the first dose of study medication will contribute to the derivation of the baseline value.

Unscheduled measurements collected post baseline will not be included in by-visit summaries but will contribute to the potentially clinically significant values for vital signs and labs and best/worst case value where required (e.g. shift table).

In the case of a retest (same visit number assigned), the latest available measurement for that visit will be used for by-visit summaries.

Listings will include scheduled, unscheduled, retest and early discontinuation data.

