16.2.1. Blood Sodium Levels

In addition to descriptive summaries of blood sodium levels and changes from baseline for each assessment time point, the number and percentage of subjects with normal baseline sodium level (i.e. >135 mEq/L) reaching ≤ 135 mEq/L but > 130 mEq/L, ≤ 130 mEq/L but > 125 mEq/L, ≤ 125 mEq/L, and > 10 mEq/L reduction (ie, < -10 mEq/L) from baseline will be summarized by arm for each evaluation time point and overall post-baseline.

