16.2.2. Laboratory Reference Ranges and Potentially Clinically Significant (PCS)

Quantitative laboratory measurements will be compared with the relevant laboratory reference ranges in SI units and categorized as:

Low: Below the lower limit of the laboratory reference range.

Normal: Within the laboratory reference range (upper and lower limit included).

High: Above the upper limit of the laboratory reference range.

Similarly, sponsor defined- PCS laboratory results will be identified using the criteria in Appendix 3.

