16.3. ECG Evaluations

The number and percentage of subjects with ECG results will be presented as Normal, Abnormal and Not Evaluable. A subject will be counted in the worst result for the post-baseline value.

ECG results will be presented in a data listing.

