16.4. Vital Signs

Vital signs (supine systolic and diastolic blood pressures, respiratory rate, pulse rate, and oral temperature) and weight will be summarized using descriptive statistics at baseline and each evaluation visit. Change from baseline will be included in this presentation as well. In addition, the number and percentage of subjects with vital sign PCS criteria in Table 4 will be presented.

Data listings of vital signs and PCS criteria will be provided.

Table 4. Vital Signs Potentially Clinically Significant (PCS) Criteria

Variable	Unit	Low	High
Supine SBP	mmHg	< 90 mmHg AND change from baseline ≤ -20 mmHg	> 180 mmHg AND change from baseline ≥ 20 mmHg
Supine DBP	mmHg	< 50 mmHg AND change from ≤ -15 mmHg	> 105 mmHg AND change from baseline ≥ -15 mmHg
Supine Pulse rate	beats/min	< 50 bpm AND change from baseline ≤ -15 bpm	> 120 bpm AND change from baseline ≥ 25 bpm

Variable	Unit	Low	High
Weight	Kg	percentage change from baseline \leq -7.0 %	percentage change from baseline \geq 7.0 %

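### The worst-ECG count, and to a lesser extent the laboratory PCS counts, take in abnormalities already present before the first dose, because neither is set against baseline

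*SAP*

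**What the plan says.** **ECG.** SAP section 16.3 reports the number and percentage of subjects as Normal, Abnormal or Not Evaluable and adds: "A subject will be counted in the worst result for the post-baseline value". Besides this count it plans only a listing. It describes no baseline tabulation and no shift.

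**Laboratory.** SAP section 16.2 says "Overall summary of the post-baseline PCS will be presented" and "The number and percentage of subjects with PCS criteria will be summarized by arm". The same summary is repeated by age group, race group, gender, baseline antiepileptic drugs (AEDs) and number of baseline AEDs. Section 16.2.2 gives the definition: "sponsor defined- PCS laboratory results will be identified using the criteria in Appendix 3". The Appendix 3 limits are absolute values or multiples of the upper limit of normal (ULN), and none mentions baseline. Under section 6.4, unscheduled post-baseline measurements "will contribute to the potentially clinically significant values for vital signs and labs".

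**Where the SAP does refer to baseline.** Section 16.2.1 limits the sodium categories to subjects whose baseline sodium is above 135 mEq/L. In Table 4 (section 16.4) the low systolic criterion reads "< 90 mmHg AND change from baseline ≤ -20 mmHg"; the other blood pressure and pulse criteria have the same two-part form, and weight uses percentage change.

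**The concern.** Both arms receive ESL and the SAP plans no comparison between them. The subject's own baseline is therefore the only internal reference for deciding whether an abnormality appeared on treatment. A count that ignores it adds subjects who arrived with the abnormality to subjects who developed it.

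At stake is how two sets of safety percentages are read. The laboratory set is also broken down by baseline AED. Those subjects had been on a stable AED regimen for at least 28 days before screening, so a deviation that predates ESL would still appear in an ESL table. The primary endpoint is not affected.

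**Working it through.** The plan states no figure here, so there is nothing to reproduce. The check is a comparison of the rules, followed by an illustration.

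**1. Is there a baseline condition?**

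| Output | Rule | Baseline used? |
|---|---|---|
| ECG result (16.3) | Worst post-baseline category | No |
| Laboratory PCS (16.2, Appendix 3) | Any post-baseline value meeting a fixed limit | No |
| Sodium categories (16.2.1) | Subjects with normal baseline only | Yes |
| Vital-sign PCS (16.4, Table 4) | Limit plus change from baseline; percentage change for weight | Yes, with one exception |

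The exception is high diastolic pressure, where the change limit is printed as ≥ -15 mmHg. A subject with no change satisfies that.

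**2. Can a subject enter already abnormal?**

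- *ECG: yes.* Exclusion 18 removes abnormal ECGs the investigator considers clinically significant, and QTcF of 450 msec or more. Other abnormal ECGs may enter, and protocol Appendix II provides for abnormalities marked not clinically significant.
- *Sodium, ALT/AST and WBC: largely no.* Exclusion 17 names sodium below 130 mEq/L, ALT or AST above 2 × ULN and WBC below 3,000 cells/mm³. The PCS limits are more extreme: sodium at or below 126 mmol/L, ALT or AST at or above 3 × ULN, WBC at or below 2.8 × 10⁹/L.
- *Other laboratory parameters: possible.* Neutrophils, hemoglobin, hematocrit, calcium, glucose and uric acid have PCS limits but no numeric entry limit, and the thyroid exclusion is worded without numbers. Exclusion 17 and protocol section 12.2 also bar laboratory results judged clinically relevant or significant, but that is a judgement and not the Appendix 3 limit.

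**3. Do other outputs show whether the finding is new?** Laboratory shift tables use low, normal and high against the reference range. A subject who is PCS-high at both times appears as high to high. So does a subject mildly high at baseline who becomes PCS-high. The table cannot tell them apart. For ECG there is only the listing.

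**4. Size.** Let b be the share abnormal at baseline, s the share of those still abnormal post-baseline, and e the new-onset rate among subjects not abnormal at baseline. Then:

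- planned percentage = b·s + (1 − b)·e
- treatment-emergent percentage = e
- share of counted subjects who are pre-existing = b·s / [b·s + (1 − b)·e]

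The documents give none of these rates, so all values of b, s and e below are assumptions. The arm size of about 50 is from SAP section 3.1.

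| b | s | e | Planned | Emergent | Pre-existing share |
|---|---|---|---|---|---|
| 2% | 80% | 0% | 1.6% | 0% | 100% |
| 2% | 80% | 2% | 3.6% | 2% | 45% |
| 10% | 100% | 2% | 11.8% | 2% | 85% |
| 30% | 100% | 2% | 31.4% | 2% | 96% |
| 30% | 100% | 5% | 33.5% | 5% | 90% |

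Third row in full: 0.10 × 1 + 0.90 × 0.02 = 0.118, or 5.9 of 50, against 0.9 of 45 = 2%. Over b from 2% to 30%, s from 80% to 100% and e from 0% to 5%, the planned figure runs from 1.6% to 33.5% while the emergent rate runs from 0% to 5%.

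Per persisting case: 1/50 = 2 percentage points. At the protocol's arm sizes it would be 1/93 = 1.1 or 1/97 = 1.0.

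**The case against.** These counts are not the main laboratory output. The stated laboratory endpoint is change from baseline, which section 16.2 summarises in full. ECG is not a listed safety endpoint; the protocol promised only a listing of ECG abnormalities, so the count is an addition. Everything is descriptive. Clinically significant findings after dosing are recorded as adverse events, and investigators review ECGs for change from previous tracings. Where a PCS limit lies outside the reference range, a subject with baseline PCS cannot be in the normal-baseline row of a shift table. Laboratory tests and ECGs are scheduled only at screening and at Visit 9 or early discontinuation, so the listings allow a subject-level check. Finally, the output templates are not in the documents, and a baseline column there cannot be ruled out.

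Most of this stands, and it is why the laboratory part is secondary. It does not supply the missing condition: the SAP text describes no output that separates new from old PCS values, and for ECG no summary by baseline status.

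Several stronger readings are tempting but unsupported:

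- A reader might infer that ECG percentages by subgroup are inflated too. Section 16.3 plans no ECG subgroup tables; only the laboratory PCS summary is broken down.
- A reader might infer that the SAP presents these counts as drug effects. Its label is post-baseline, which is accurate. Attribution to ESL would be the reader's step, though a natural one without a control.
- A reader might infer that every vital-sign PCS criterion requires a worsening. The high-diastolic cell as printed does not.

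**Conclusion.** The concern holds for both counts as the SAP is written, and mainly for ECG: entry with an abnormal tracing is expressly possible and only a listing shows its baseline. For laboratory PCS it holds to a lesser extent, because entry criteria largely remove baseline cases of low sodium, raised ALT/AST and low WBC, and other outputs show part of the baseline status.

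The size cannot be stated from the documents. What is firm is the arithmetic of about 2 percentage points per persisting baseline case, assuming 50 evaluable subjects per arm. The 11.8% against 2% example rests on assumed rates, and it would be wrong to infer that any such baseline prevalence is expected here. A pre-existing abnormality is counted only if it is present again after dosing. The change is worth making because it is cheap and these tables have no comparator; it bears on interpretation of safety data, not on the primary result.

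**What to change.** **ECG (SAP 16.3).** Add a shift table by arm from baseline to worst post-baseline result, Normal or Abnormal. Show Not Evaluable on its own line and do not rank it as a result; the SAP does not say where it falls in the worst-result rule. A two-category shift will not show a new abnormality in a subject already abnormal at baseline, so keep the listing for that.

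**Laboratory PCS (SAP 16.2).** Keep the all-subject post-baseline count and add a treatment-emergent count, overall and in the planned subgroups:

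- Numerator: subjects who did not meet the criterion at baseline and met it post-baseline.
- Denominator: subjects with a baseline value not meeting the criterion and at least one post-baseline value.
- Separate line: subjects who met the criterion at baseline.

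Keeping both counts means that subjects already meeting a criterion are not lost from view.

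**Cost.** SAP wording and two modified table shells, using data already scheduled at screening and at Visit 9 or early discontinuation. The treatment-emergent denominators will be slightly smaller. No protocol change is needed. If the templates already hold a baseline column or shift, the SAP text need only say so.

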16.2.1. Blood Sodium Levels

In addition to descriptive summaries of blood sodium levels and changes from baseline for each assessment time point, the number and percentage of subjects with normal baseline sodium level (i.e. >135 mEq/L) reaching ≤ 135 mEq/L but > 130 mEq/L, ≤ 130 mEq/L but > 125 mEq/L, ≤ 125 mEq/L, and > 10 mEq/L reduction (ie, < -10 mEq/L) from baseline will be summarized by arm for each evaluation time point and overall post-baseline.

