16. Subject has a major medical illness other than epilepsy that would prevent safe participation in this study, at the discretion of the Investigator, including (but not limited to) cardiac disease, thyroid disease, hepatic or renal impairment, endocrine or metabolic disease, gastrointestinal disease, or hematologic disease. Note: Active medical conditions that are minor or well-controlled are not exclusionary if they do not affect risk to the subject or the study results. If the effect of the condition in regard to the risk to the subject or to the study results is unclear, the Medical Monitor should be consulted.
17. Subjects with clinically relevant laboratory abnormalities at screening (eg, sodium < 130 mEq/L, alanine transaminase (ALT) or aspartate transaminase (AST) > 2.0 times the upper limit of the normal, white blood cell [WBC] count $< 3,000$ cells/mm 3 , estimated creatinine clearance < 50 mL/min, or has values for thyroid testing (free triiodothyronine (T3), free thyroxine (T4), thyroid stimulating hormone [TSH]) indicating the presence of significant thyroid dysfunction.
18. Subject has a history or presence of abnormal electrocardiogram (ECG), which in the Investigator's opinion is clinically significant or QT interval corrected for heart rate using the Fridericia method (QTcF) of ≥ 450 msec per screening ECG.

19. Subject has second- or third-degree atrioventricular block that is not corrected with a pacemaker.
20. Subjects who meet the Diagnostic and Statistical Manual of Mental Disorders, 5th edition text revision defined criteria for major depressive episode within the last 6 months. Subjects with mild, chronic depression without recent hospitalization who are being maintained on a stable dose of a single antidepressant are acceptable.
21. Subject has an active suicidal plan or intent (in the Investigator's opinion) in the past 4 weeks prior to screening.
22. Subject has a history of suicide attempt in the last 2 years prior to screening.
23. Subject has other major psychiatric disorders.
24. Subjects who are not able to complete the diaries in the Investigator's opinion.
25. Subject has a history of alcohol or substance abuse within 2 years prior to screening for study participation, or subjects currently using alcohol, drugs of abuse, or any prescribed or over-the-counter medication in a manner, which, in the opinion of the Investigator, indicates abuse.

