15.3.8.4. Blood Sodium Levels

In addition to descriptive summaries of blood sodium levels and changes from baseline for each assessment time point, the percent of subjects with normal baseline sodium level reaching ≤ 135 mEq/L but > 130 mEq/L, ≤ 130 mEq/L but > 125 mEq/L, ≤ 125 mEq/L, and > 10 mEq/L reduction (ie, < -10 mEq/L) from baseline will be summarized by time point.

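### SAP 16.2.1 counts low sodium only when baseline is above 135 mEq/L, so a fall from 131-135 to 127-130 is in neither threshold table

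*SAP*

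**What the plan says.** **Sodium categories.** Protocol 15.3.8.4 plans to report "the percent of subjects with normal baseline sodium level reaching" each of several low-sodium bands, without defining normal. SAP 16.2.1 adds the number: "subjects with normal baseline sodium level (i.e. >135 mEq/L". The bands are <=135 but >130, <=130 but >125, and <=125 mEq/L. The large-fall category sits in the same sentence and under the same restriction: "reduction (ie, < -10 mEq/L) from baseline will be summarized by arm".

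**Entry.** Protocol 8.2, exclusion 17, covers "Subjects with clinically relevant laboratory abnormalities at screening (eg, sodium < 130 mEq/L". The figure is given as an example. Protocol 12.2 also bars entry for a screening result judged clinically significant and not covered by the inclusion criteria. A value of 130-135 is therefore neither automatically excluded nor guaranteed entry.

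**Other laboratory summaries.** SAP 16.2 plans a PCS table: "The number and percentage of subjects with PCS criteria will be summarized by arm". SAP Appendix 3 sets the low sodium limit at 126 mmol/L or below. SAP 16.2 also plans shift tables giving the "percentage of subjects with laboratory test values below, within, and above the normal range". SAP 16.2.2 defines normal there as the laboratory reference range with both limits included. Neither table restricts baseline. Protocol 12.2 has clinically significant abnormal laboratory values recorded as adverse events.

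**The concern.** A restriction to normal baseline makes sense for the <=135 row, because a subject already at or below 135 cannot newly reach it. It has no such logic for the other rows. A subject entering at 133 can newly reach <=130 or <=125, or fall by more than 10, and is counted in none of these.

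Sodium is the only laboratory analyte with its own analysis section, so readers will go to that table for the frequency of low sodium on treatment. It leaves out the subjects who start closest to the thresholds. A subject going from 132 to 128 crosses the level that the protocol itself offers as an example of a clinically relevant abnormality, yet appears in neither table that counts against a fixed sodium threshold. Laboratory tests are scheduled only at screening and at Visit 9 or early discontinuation, so there is little chance that a later scheduled sample brings that subject into a count.

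**Working it through.** The plan states no figure on this point, so there is nothing to reproduce. The check takes each combination of baseline and post-baseline sodium and asks which table counts it.

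**Inputs** (b = baseline, p = post-baseline; for sodium 1 mmol/L = 1 mEq/L)
- Sodium table (SAP 16.2.1): counted only if b > 135.
- PCS Low (SAP Appendix 3): p <= 126, any b.
- Shift table (SAP 16.2, 16.2.2): Low if below the laboratory's lower limit of normal (LLN). The LLN is not given, so 132 to 136 is tried as an assumption.
- Baselines not automatically excluded but outside the sodium table: 130 to 135.

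**1. Falls to 127-130.** In whole numbers, baselines 131 to 135 give 5 x 4 = 20 combinations. Baseline 130 gives 3 more (127, 128, 129), for a total of 23.
- Sodium table: b > 135 is never met, so 0 of 23 are counted.
- PCS Low: the lowest value is 127, above 126, so 0 of 23 are counted.
- In steps of 0.1 (p above 126, up to 130), neither table counts any of the 2039 combinations.

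**2. How the shift table shows those 23.**

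| Assumed LLN | Low to Low | Normal to Low |
|---|---|---|
| 132 | 7 | 16 |
| 133 | 11 | 12 |
| 134 | 15 | 8 |
| 135 | 19 | 4 |
| 136 | 23 | 0 |

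The three combinations from baseline 130 are Low to Low throughout. For baselines 131-135 alone, the Low to Low counts are therefore 4, 8, 12, 16 and 20 of 20. These are counts of possible values, not of expected subjects.

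**3. Larger falls from b <= 135.** A fall of more than 10 means p < b - 10 <= 135 - 10 = 125. Every such value is below 125 and so meets PCS Low: 105 of 105 whole-number combinations with p down to 105, and 8925 of 8925 in steps of 0.1. A fall to <=125 also lies within <=126. These subjects are in the PCS count but not in the <=125 or >10-fall rows of 16.2.1. For example, 134 to 123 is a fall of 11 to below 125: PCS Low counts it, and 16.2.1 counts it in neither row.

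**4. Size of one omitted case.** SAP 3.1 plans about 50 subjects per arm: 1/50 = 2.0 percentage points. At the protocol's 93 and 97 it would be 1/93 = 1.1 and 1/97 = 1.0.

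**5. Two meanings of normal.** SAP 16.2.1 uses >135, while SAP 16.2.2 uses the laboratory range with limits included. If the LLN is 135 or lower, a baseline of exactly 135 is normal in the shift table and not normal in the sodium table.

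**The case against.** The strongest reply is that 16.2.1 measures something definite: onset of low sodium in subjects whose sodium was normal. Protocol 15.3.8.4 prespecified that population, the SAP follows it, and the row is labelled accordingly. This stands. A reader might infer that the reported incidence is biased downwards, but the documents do not support that, since for its stated population the figure is right. What remains is that the plan has no threshold-based count of new falls to <=130 among the other subjects who may enter.

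A reader might also infer that subjects at 130-135 who fall by more than 10 mEq/L are in no count at all. That is wrong: such a fall always ends below 125 and is always PCS Low.

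Nor does a fall to 127-130 show only in the mean change. The subject is in the shift table, in listings that flag out-of-range results, in descriptive statistics that include the minimum and 25th percentile (SAP 6.1), and in the adverse event tables if the value is judged clinically significant. These outputs limit the gap without closing it. The shift table may show no worsening, listings and descriptive statistics give no incidence, and the adverse event route depends on investigator judgement.

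Finally, the group may be small or empty, because a screening value judged clinically significant can bar entry. That also stands.

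**Conclusion.** The gap is real and narrow. A fall from 131-135 to 127-130 is counted in neither the sodium category table nor the PCS table, and the shift table may show it only as Low to Low. Falls to <=125, or by more than 10 mEq/L, from a baseline of 135 or less are counted as PCS Low but not in the matching sodium rows, so two tables in the same report can disagree without explanation.

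The number of subjects affected cannot be estimated, because the documents give neither a baseline sodium distribution nor an event rate. Each omitted case is about 2 percentage points of an arm of about 50. The shift-table result rests on the assumed LLN of 132 to 136. The summaries are descriptive and no test is affected. The change is worth making because the data are already collected and the restriction has a reason for only one of the four rows.

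**What to change.** In SAP 16.2.1, keep the baseline >135 restriction for the <=135 row and add:
- <=130 among subjects with baseline >130;
- <=125 among subjects with baseline >125;
- a reduction of more than 10 mEq/L among all subjects with a baseline and a post-baseline value.

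Alternatively, cross-tabulate baseline category (>135, >130 to 135, <=130) by worst post-baseline category, together with the unrestricted >10 mEq/L row. This also covers a baseline of exactly 130, which exclusion 17's example does not exclude and which the <=130 row above would still omit. Either way, state each row's denominator, and say how normal in 16.2.1 relates to the reference range in 16.2.2.

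The cost is SAP wording and a few descriptive rows, with no new samples or visits. The rows go beyond the protocol's normal-baseline summary, so they should be noted in SAP 3.4.2.
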